#### **7.4.2. Medical Records and General Pediatric Evaluation**

Upon completion of the outcome interview, each woman is sent a packet electronically or by hard copy mail containing research HIPAA compliant medical records release forms for the delivery hospital, obstetrician, pediatrician, and vaccine provider if applicable. For women whose pregnancies have ended in stillbirth, records release forms are mailed for prenatal diagnosis (if applicable), pathology or autopsy reports if available. Each eligible woman is asked to sign (electronically or by wet signature) the medical records release forms, as well as UCSD HIPAA Authorization Addendum (if they or their infant receives medical care at UCSD/Rady Children's hospital) and to return them along with the pregnancy exposure diary form.

Upon receipt of the signed medical records release forms, a standard physical evaluation form is mailed to each pediatrician or other physician responsible for the care of each live born infant through 2 months of age.

Medical records are reviewed by trained abstractors to supplement information self-reported by the participant related to vaccine exposure, outcomes, prenatal tests, and medical history.

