### 7.2.1. Inclusion/exclusion criteria

All participants must meet the following criteria to be eligible for inclusion in the study:

- Reside in the US at the time of enrollment
- Enrolled in the OTIS/MotherToBaby Pregnancy Registry and currently pregnant at the time of enrollment on or after 08 March 2004
- Pregnancy ending in either livebirth or stillbirth
- Availability of medical records for that pregnancy including from obstetric provider, hospital of delivery and pediatric provider

The study sample will consist of approximately 600 participants in each cohort that have previously been enrolled in the OTIS/MotherToBaby Pregnancy Registry before the end of pregnancy, have completed their pregnancies with either a livebirth or stillbirth outcome, and have sufficient medical record and exposure data to meet the study objectives. An additional 1,800 participants (900 in each cohort) will be enrolled over four years; these participants will enroll before the end of pregnancy, have completed their pregnancies with either a livebirth or stillbirth outcome, and have sufficient medical record and exposure data to meet the study objectives.

- Selection for consideration for inclusion of the 600 pregnancies in each cohort from those previously enrolled in the OTIS/MotherToBaby Pregnancy Registry will be made solely on the following criteria irrespective of pregnancy outcome
  - Pregnancy continuing as of the 1st day of the 27th week of gestation
  - Availability of data on Tdap vaccination status on or after the 1st day of the 27th week of gestation
  - If vaccinated, data available to document Tdap vaccination brand
  - Availability of the required medical records from obstetric, hospital and pediatric providers
  - Selection starting with most recent year of enrollment until sample size is met

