**Table 3 Timing of Cohort Enrollment, Interviews, Examinations, and Medical Records**

	Any Time In Pregnancy	20-22 Weeks' Gestation 	32-34 Weeks' Gestation 	0-6 Weeks Post-Delivery	0-2 Months Post-Delivery
Referral 	√				
Enrollment and Consent 	√				
Enrollment Interview 	√				
Interim Interview I		√			
Interim Interview II			√		
Pregnancy Outcome Interview and Request for Medical Records				√	
Medical Record Acquisition and Review					√

 Participants may enroll in the study any time during pregnancy.

 If participant is enrolled and Intake Interview is conducted after 18 weeks' gestation, only one interim interview is conducted during pregnancy at 32-34 weeks gestation.

 If participant is enrolled and Intake Interview is conducted at 30 weeks' gestation or after, no Interim Interview is collected.

Medication or vaccine exposures entered into the database are coded using the Slone Drug Dictionary. Data are recorded on hard copies of forms and these records are retained by OTIS/MotherToBaby at the Research Center. These forms are considered the primary data sources for studies and can be adapted to add new data elements. Data from these forms are extracted and entered into a customized OTIS/MotherToBaby study database located in the Research Center.

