### 7.4.1. Maternal Interviews

Below is a detailed description of each interview as conducted under the OTIS/MotherToBaby Pregnancy Registry protocol:

- Intake/Enrollment Interview:** A structured maternal intake telephone interview is conducted at enrollment by a trained Research Associate from the OTIS/MotherToBaby Research Center. This interview includes questions on the following: pregnancy history, including major congenital malformations, genetic disorders, number of live births, and multiple gestations; current health history; pre-pregnancy weight and height; socioeconomic and demographic information including maternal and paternal occupation, education and ethnicity; income category; current medication use, both prescription and over the counter; other environmental or occupational exposures, alcohol, tobacco, caffeine and illicit drug

use, vaccine exposure prior to and during pregnancy; current pregnancy complications including illnesses; family history of adverse pregnancy outcomes, including major congenital malformations and genetic disorders; names and addresses of health care providers; and vaccine use during pregnancy. To supplement future interviews and improve recall, participants are given a pregnancy exposure diary to record any additional exposures (medications, vaccinations, vitamins, etc.) or events as the pregnancy progresses. Each woman is also sent the informed consent document and the US Health Insurance Portability and Accountability Act (HIPAA) Authorization Addendum (when applicable) via electronic signature or paper, and a research HIPAA compliant obstetric medical record release form.

- **Interim Interviews I and II:** Telephone interviews are conducted at 20-22- and 32-34-weeks' gestation (if enrolled before the interview interval) by a trained Research Associate from the OTIS Research Center. Women who have enrolled prior to 18 weeks post-LMP will be interviewed by telephone at 20-22 weeks post-LMP, 32-34 weeks post-LMP and within 2 to 6 weeks after the expected due date. Women who have enrolled between 19 and 20 weeks post-LMP will be interviewed at 32-34 weeks post-LMP (See [Table 3](#)). These interviews are intended to update records of pregnancy exposures (medications, vaccinations, vitamins, etc.), results of prenatal tests, events of interest since last interview (including if the pregnancy has ended prior to the expected due date), and contact information.

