#### **7.5. Study size**

[figure not shown]
The target sample sizes in each of the study cohorts are as follows:

- 1,500 women exposed to *Boostrix* on or after the 1st day of the 27th week of gestation through the end of pregnancy
- 1,500 women unexposed to any Tdap vaccine throughout their pregnancy

Including an estimated 600 eligible participants per cohort already enrolled in the OTIS/MotherToBaby Pregnancy Registry, enrollment of 1,500 participants in each of the cohort groups is planned for completion within 4 years. Participants are eligible to enroll at any time in pregnancy including prior to the gestational timing of the recommended Tdap vaccine. (Examples of gestational timing of enrollment, exposure, and outcome are shown in [Figure 1](#) and [Figure 2](#)). Thus, some initially enrolled pregnancies will no longer be eligible for analysis due to pregnancy losses (spontaneous abortion, elective termination, stillbirth prior to the 27th week of gestation, or lost-to-follow-up). Additionally, some pregnancies will not be eligible for inclusion due to failure to release medical records. The final sample size of 1,500 per cohort will represent all pregnancies that met full inclusion/exclusion criteria. From this sample of livebirths and stillbirths, we conservatively estimate that at least 1,425 in each cohort will represent pregnancies ending in liveborn singleton infants.

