There may be potential biases in individuals who do or do not meet the requirement of releasing medical records in order to be eligible for inclusion in the study. Comparisons on key baseline covariates for those who were excluded from eligibility solely on the basis of medical records availability will be compared to those included in the study.

There may be potential biases involved in changing definitions of selected study outcomes over time. For example, criteria for preeclampsia/eclampsia have been modified in recent years. A sensitivity analysis (below) is planned to address this issue.

There can also be a "healthy vaccinator" bias which is a potential confounder that may be difficult to control for. In other words, women who elect to receive the *Boostrix* vaccine may have other lifestyle characteristics that are unmeasured or poorly measured that are associated with the pregnancy and infant outcomes of interest. A sensitivity analysis (below) to address this issue.

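### The delivery-hospital and pediatric releases needed for inclusion are sent only after the outcome interview, so inclusion can depend on the outcome; the protocol describes this bias but carries it into no effect estimate

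*Protocol*

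**What the plan says.** Section 7.2.1 sets this criterion for all participants: "Availability of medical records for that pregnancy including from obstetric provider, hospital of delivery and pediatric provider". The criteria for each cohort repeat it. Both cohorts must also agree, while pregnant, to release of medical records.

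The forms go out at two times. At intake each woman receives "a research HIPAA compliant obstetric medical record release form" (Section 7.4.1). The rest follow the end of pregnancy (Section 7.4.2): "Upon completion of the outcome interview, each woman is sent a packet electronically or by hard copy mail containing research HIPAA compliant medical records". That packet holds the "release forms for the delivery hospital, obstetrician, pediatrician, and vaccine provider if applicable". Table 3 agrees: its row "Pregnancy Outcome Interview and Request for Medical Records" falls 0 to 6 weeks after delivery.

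Section 7.5 gives the consequence: "some pregnancies will not be eligible for inclusion due to failure to release medical records".

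The protocol recognises that the release requirement may introduce bias. Section 7.7.1 plans "Comparisons on key baseline covariates for those who were excluded from eligibility solely on the basis of medical records availability". Section 7.9 goes further and commits to comparing women who do not return records on demographics and on selected outcomes. Section 7.7.2 lists sensitivity analyses for diagnostic criteria that changed over time, for healthy-vaccinator bias and for major birth defects, and possible stratified analyses of prior against new enrollees. None concerns women excluded for missing records.

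**The concern.** An eligibility criterion is met or failed by an act that follows the end of pregnancy. By then the woman knows whether the birth was preterm, the infant small or the pregnancy a stillbirth. That knowledge could make her less willing to sign (distress) or more willing (a wish to have a suspected vaccine effect examined). The second motive could arise only in the vaccinated cohort.

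If outcome-related release differs between cohorts, the relative risks and the preterm hazard ratio are distorted. Propensity weighting on baseline variables cannot be relied on to correct this, because the selection acts through the outcome itself. In a safety study the distortion matters in both directions: a real increase can be hidden, or a false one created. If release depends on outcome equally in the two cohorts, the ratio is essentially preserved but the absolute risks in each cohort are still wrong.

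**Working it through.** **Sequence.** The protocol states no figure to reproduce, so the first check is the order of events.

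1. Records required for inclusion: obstetric, delivery hospital, pediatric (Section 7.2.1).
2. Release sent at intake: obstetric only (Section 7.4.1).
3. Releases sent after the outcome interview: delivery hospital, obstetrician, pediatrician and, if applicable, vaccine provider (Section 7.4.2, Table 3).
4. No release means not eligible (Section 7.5).
5. By step 3 the woman has been interviewed on delivery date, birth size, live birth or stillbirth, and exposures since the previous interview (Section 7.4.1); vaccines are asked about directly (Section 7.3.1).

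Two of the three required sources therefore depend on a signature requested after the outcome is known, and the women who do not sign have already reported the main outcomes by interview.

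**Size.** Inputs: event risk p = 10%, the comparator rate for preterm delivery and SGA in Table 4. Release probabilities are assumptions, since the protocol gives none: s0 = 0.85 among non-cases in both cohorts, and s1 among cases as shown. In each cohort:

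observed risk = p·s1 / (p·s1 + (1 − p)·s0), with (1 − p)·s0 = 0.90 × 0.85 = 0.765

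- s1 = 0.80: 0.080 / 0.845 = 0.0947
- s1 = 0.75: 0.075 / 0.840 = 0.0893
- s1 = 0.65: 0.065 / 0.830 = 0.0783

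| Case release, exposed v unexposed | Observed RR (true RR 1.0) |
|---|---|
| 80% v 65% | 0.0947 / 0.0783 = 1.21 |
| 80% v 75% | 0.0947 / 0.0893 = 1.06 |
| 75% v 75% | 0.0893 / 0.0893 = 1.00 |
| 65% v 75% | 0.0783 / 0.0893 = 0.88 |

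Reversing the first row (65% v 80%) gives 0.0783 / 0.0947 = 0.83.

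**Absolute risk.** With 75% case release in both cohorts the RR stays at 1.00, but the observed risk is 8.9% instead of 10%.

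**A masked signal.** Take a true RR of 1.4, the value in Table 4 for preterm delivery and SGA, and assume 90% release for everyone except exposed cases, who release at 80%. The exposed risk is 0.14 × 0.80 / (0.14 × 0.80 + 0.86 × 0.90) = 0.112 / 0.886 = 0.126. The unexposed risk stays at 0.10, so the observed RR is 1.26.

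**Condition for bias.** The odds ratio is multiplied by (s1/s0 in exposed) / (s1/s0 in unexposed). If that ratio is 1 the odds ratio is unchanged and the RR nearly so: with 70% case and 90% non-case release in both cohorts, a true RR of 1.4 appears as 1.41.

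**The case against.** **Recognised bias.** A reader might infer that the protocol overlooked this bias. It did not. Section 7.7.1 names it, and the comparison on selected outcomes in Section 7.9 bears directly on whether release depends on outcome. What remains is narrower: the comparison is descriptive, it is not said to be made by cohort, Section 7.7.1 limits it to baseline covariates, and no effect estimate uses it.

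**No evidence of differential release.** A reader might infer that the planned estimates are biased. The documents do not support that. They give no release rates, and distress after a poor outcome could act alike in both cohorts, leaving the ratio essentially intact. A gap of 5 points moves the RR only to 1.06. This objection stands, so the finding is conditional.

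**Agreement while pregnant.** Consent to release records is an entry condition, and Section 8.1 says participants are asked to sign for release from all three sources, without giving a time. This softens the concern but does not bring the delivery-hospital and pediatric signatures forward, and Section 7.5 still expects some women not to release.

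**Design rationale.** It is tempting to say that this refutes the rationale in Section 7.1 that mothers enrol before the outcome is known. That section makes no claim of protection from selection, and Section 7.9 names selection among volunteers as the main limitation. The stronger charge fails.

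**Matter for the SAP.** Further sensitivity analyses may be specified there, and the SAP is not at hand. But the eligibility rule and the timing of the forms are fixed by the protocol. The missing-data sensitivity analyses that Section 7.6.1 defers to the SAP concern missing values, not women removed by eligibility.

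**Conclusion.** The point holds as a possibility that the protocol leaves unhandled. Inclusion is partly settled after the outcome is known, and the response is descriptive only. Under the assumed release rates the three scenarios with unequal case release give an observed RR of 0.88 to 1.21 for a true value of 1.0 (0.83 if the largest gap is reversed). The upper figure is about half of the excess risk in the RR of 1.4 that Table 4 gives as detectable for preterm delivery and SGA. Small gaps matter little, and equal gaps do not bias the ratio at a true RR of 1.0. Absolute risks are biased whenever cases and non-cases release at different rates.

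The expected loss to follow-up below 5% (Section 7.9) does not settle the matter. Non-release is a separate step, and the protocol gives no figure for it.

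**What to change.** 1. **Add a sensitivity analysis to Section 7.7.2** of preterm birth, SGA and stillbirth that includes otherwise eligible women excluded solely for missing records. Classify exposure and outcome from the interviews plus any obstetric record already released. State that for this analysis the record confirmation required for unexposed status (Section 7.3.1, Table 1) and for the outcomes (Table 1) is relaxed. Report it beside the main result. If the SAP already contains such an analysis, a reference to it is enough.
2. **Align Section 7.7.1 with Section 7.9**, so that interview-reported outcomes of releasers and non-releasers are compared within each cohort, with the number and proportion not releasing.
3. **Optionally, for new enrollees, request all releases before delivery:** delivery hospital, vaccine provider and, where already chosen, pediatrician. Keep the post-delivery packet for missing or changed providers.

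The third step alone would not be a cure. Some pediatric releases would still follow delivery, and it cannot reach the roughly 600 prior enrollees per cohort (600 / 1,500 = 40%).

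**Cost.** One further analysis of data already collected, with its own definitions, and for the third step an ethics-approved change in when existing forms are sent. The added pregnancies rest largely on maternal report, so misclassification is possible, especially of unexposed status and vaccine brand; the analysis should stay secondary. Some releases signed before delivery will need re-signing.

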#### **7.4.3. Scientific Advisory Board**

An existing external Scientific Advisory Board under the Vaccines and Medication in Pregnancy Surveillance System (VAMPSS) provides oversight for the study and reviews study summary data on an annual basis. Members of the Board provide advice to the Registry investigators on interpretation of the data and provide advice on strategies for the dissemination of information regarding the study.

The VAMPSS Scientific Advisory Board is managed by the American Academy of Allergy, Asthma and Immunology. The Scientific Advisory Board is comprised of membership representing specialization in maternal fetal medicine, biostatistics, vaccine epidemiology, and representation from the Centers for Disease Control, National Institutes of Health/Child Health Institute, the American Academy of Pediatrics, and a consumer representative. The Board is chaired by a designated member, and each member has one vote. A dedicated charter describes roles and responsibilities of the Board members, and members complete conflict of interest disclosures on an annual basis.

#### **7.5. Study size**

[figure not shown]
The target sample sizes in each of the study cohorts are as follows:

- 1,500 women exposed to *Boostrix* on or after the 1st day of the 27th week of gestation through the end of pregnancy
- 1,500 women unexposed to any Tdap vaccine throughout their pregnancy

Including an estimated 600 eligible participants per cohort already enrolled in the OTIS/MotherToBaby Pregnancy Registry, enrollment of 1,500 participants in each of the cohort groups is planned for completion within 4 years. Participants are eligible to enroll at any time in pregnancy including prior to the gestational timing of the recommended Tdap vaccine. (Examples of gestational timing of enrollment, exposure, and outcome are shown in [Figure 1](#) and [Figure 2](#)). Thus, some initially enrolled pregnancies will no longer be eligible for analysis due to pregnancy losses (spontaneous abortion, elective termination, stillbirth prior to the 27th week of gestation, or lost-to-follow-up). Additionally, some pregnancies will not be eligible for inclusion due to failure to release medical records. The final sample size of 1,500 per cohort will represent all pregnancies that met full inclusion/exclusion criteria. From this sample of livebirths and stillbirths, we conservatively estimate that at least 1,425 in each cohort will represent pregnancies ending in liveborn singleton infants.

### Figure 1 Example of Participant Qualified for Boostrix-exposed

Figure 1. Example of Participant Qualified for Boostrix-Exposed

### Figure 2 Example of Participant Qualified for Tdap unexposed

Figure 2. Example of Participant Qualified for Tdap Unexposed

[figure not shown]

Table 4 gives the minimum detectable effect size with 80% power for 2 of the primary endpoints and for 1 of the secondary endpoints. Other secondary endpoints are expected to be less frequent than 1-2% in the comparator group. Therefore, statistical power will be limited and only high relative risks will be detectable for these secondary endpoints. This also applies to the primary outcome of stillbirth.

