## Data Analysis

Demographic and other maternal characteristics will be compared between the two cohorts. The outcome analyses include:

1. comparison of proportion of PTBs among those enrolled prior to 37 weeks' gestation and resulting in a live born singleton infant between the *Boostrix*-exposed cohort and the comparison cohort by calculating hazard ratios and associated 95% confidence intervals.
2. comparison of proportion of stillbirths between the *Boostrix*-exposed cohort and the comparison cohort by calculating relative risks and associated 95% confidence intervals.
3. comparison of proportion of SGA infants ( $\leq 10^{\text{th}}$  centile for sex and gestational age) on birth weight, length, and head circumference among live born singletons between the *Boostrix*-exposed cohort and the comparison cohort by calculating relative risks and associated 95% confidence intervals.
4. comparison of proportion of preeclampsia/eclampsia diagnosed after the 1st day of the 27th week of gestation in pregnancies ending in livebirth or stillbirth between the *Boostrix*-exposed cohort and the comparison cohort by calculating relative risks and associated 95% confidence intervals.
5. comparison of proportion of cases of chorioamnionitis in pregnancies ending in livebirth or stillbirth between the *Boostrix*-exposed cohort and the comparison cohort by calculating relative risks and associated 95% confidence intervals.
6. comparison of proportion of PROM occurring after the 1st day of the 27th week of gestation in pregnancies ending in livebirth or stillbirth between the *Boostrix*-exposed cohort and the comparison cohort by calculating relative risks and associated 95% confidence intervals.
7. comparison of proportion of cases of neonatal sepsis occurring in pregnancies ending in live birth including twins or higher order multiples between the *Boostrix*-exposed cohort and the comparison cohort by calculating relative risks and associated 95% confidence intervals.

8. comparison of proportion of neonatal deaths occurring in pregnancies ending in live birth including twins or higher order multiples between the *Boostrix*-exposed cohort and the comparison cohort by calculating relative risks and associated 95% confidence intervals.

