**Table 4 Sample Size and Detectable Effect Size with 80% Power for Comparison of *Boostrix*-Exposed to Comparison**

Endpoint	N in Each Group	Rate in Comparison Group	Relative Risk	Power 
Preterm delivery	1425	10% 	1.4	80%
SGA	1425	10% 	1.4	80%
Chorioamnionitis	1469	3%	1.7	80%

 All tests are two-sided with alpha = 0.05, based on Fisher's exact test. Calculations conducted using R.

 (Ferré, 2016)

 (CDC, 2017; Nellhaus, 1968; Olsen, 2010)

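### Table 4 prints 80% power for RR 1.4 in the preterm and SGA rows; its own inputs give about 90%, with a minimum detectable RR of about 1.34, and the preterm N omits that analysis's own restrictions

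*Protocol*

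**What the plan says.** The text that introduces Table 4 in Section 7.5 states that "Table 4 gives the minimum detectable effect size with 80% power for 2 of the primary endpoints" and for one secondary endpoint. The table title and its power column repeat the 80%. Footnote 1 gives the basis: "All tests are two-sided with alpha = 0.05, based on Fisher's exact test".

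The rows are:

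| Endpoint | N per group | Comparator rate | RR | Stated power |
|---|---|---|---|---|
| Preterm delivery | 1,425 | 10% | 1.4 | 80% |
| SGA | 1,425 | 10% | 1.4 | 80% |
| Chorioamnionitis | 1,469 | 3% | 1.7 | 80% |

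The 1,425 comes from Section 7.5: "we conservatively estimate that at least 1,425 in each cohort will represent pregnancies ending in liveborn singleton infants", out of 1,500 per cohort who meet all inclusion and exclusion criteria.

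For preterm delivery, Section 7.7.1 adds two conditions. The woman must have enrolled before 37 weeks. In the exposed cohort, vaccination must also have taken place before 36 weeks and 5 days. The planned model is a Cox marginal structural model with time-dependent exposure, which yields a hazard ratio.

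The abstract (Data Analysis, item 5) describes the chorioamnionitis analysis as a "comparison of proportion of cases of chorioamnionitis in pregnancies ending in livebirth or stillbirth between the" two cohorts.

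**The concern.** Table 4 is the protocol's only quantitative statement of what the study can detect. A row that gives N, rate, RR, test and alpha leaves no free quantity, so its power can be checked. In two of the three rows, both for primary endpoints, the printed power does not follow from the other entries.

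Anyone who later interprets a null result for preterm birth or SGA will set the confidence interval against this table. They will take 1.4 as the smallest effect the study had an 80% chance of finding, when the stated inputs imply 1.34.

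The preterm row has a second problem that works in the opposite direction. Its N counts all liveborn singletons, although the analysis keeps a subset of them, and the row does not say that it is an approximation to a different model.

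**Working it through.** **Inputs.** All come from Table 4 and its footnote: two-sided alpha 0.05, Fisher's exact test, equal groups. Preterm and SGA rows: n = 1,425, p0 = 0.10, p1 = 1.4 × 0.10 = 0.14. Chorioamnionitis row: n = 1,469, p0 = 0.03, p1 = 1.7 × 0.03 = 0.051.

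**Method.** Exact power is the sum, over all pairs (x0, x1) whose two-sided Fisher p-value is at most 0.05, of Bin(x0; n, p0) × Bin(x1; n, p1). The hand check is the pooled normal formula:

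Power = Φ{ [ (p1 − p0) − 1.96·√(2·p̄(1 − p̄)/n) ] / √([p0(1 − p0) + p1(1 − p1)]/n) }, with p̄ = (p0 + p1)/2.

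**Step 1: the row that reproduces.** For chorioamnionitis the exact power is 80.4% and the minimum detectable RR at 80% is 1.696, which prints as 1.7. The method is therefore consistent with the table.

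**Step 2: the preterm and SGA rows.** By hand, p̄ = 0.12:

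- √(2 × 0.12 × 0.88/1,425) = 0.01217
- √((0.0900 + 0.1204)/1,425) = 0.01215
- (0.04 − 1.96 × 0.01217)/0.01215 ≈ 1.33, so power ≈ 90.8%

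The exact Fisher power is **89.9%**. The table prints 80%.

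**Step 3: what 80% corresponds to.** Exact Fisher power at n = 1,425 and a 10% rate:

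| RR | Power |
|---|---|
| 1.30 | 69.0% |
| 1.34 | 79.1% |
| 1.35 | 81.3% |
| 1.40 | 89.9% |

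Solving for 80% gives RR = 1.344 (1.337 by the pooled formula).

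**Step 4: rounding.** At one decimal, 1.4 is the smallest RR that reaches 80% for these two rows, because 1.3 reaches only 69.0%. For chorioamnionitis, 1.7 is likewise the smallest, because 1.6 gives 68.4%. Rounding every minimum detectable RR up to one decimal therefore reproduces all three printed RRs. What it does not reproduce is the 80% beside 1.4.

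**Step 5: how far the preterm N can fall.** The protocol does not say how many women the enrollment and vaccination-timing conditions remove. Exact power for 10% against 14% is 79.6% at 1,070 per group, 80.0% at 1,080 and 80.9% at 1,100. RR 1.4 thus keeps at least 80% power until N falls to about 1,080, a loss of (1,425 − 1,080)/1,425 = 24%. This treats the analysis as a comparison of two proportions. It allows nothing for precision lost to weighting, late entry or time-dependent exposure, none of which the protocol quantifies.

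**Step 6: chorioamnionitis N.** The analysis population is livebirths and stillbirths, which Section 7.5 puts at 1,500 per cohort. The protocol does not derive 1,469. With 1,500, RR 1.7 has 81.3% power and the minimum detectable RR is 1.687, so the printed value stays 1.7.

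**The case against.** The strongest reply is that nothing here harms the study. The discrepancy is on the safe side, and rounding up to one decimal explains every RR in the table. On preterm delivery, the printed 1.4 leaves a margin of about 24% of N for restrictions that the table does not deduct. All of this stands, and it limits the point to correcting a mis-stated power. It does not make the 80% right: the table says nothing about rounding and does not say at least 80%.

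A reader might infer more than the protocol supports:

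- **That a lower comparator rate was really used.** A rate of 8% would give 81.2% power at RR 1.4, but that value was found only by looking for one that fits. The table states 10% and cites sources for it.
- **That the chorioamnionitis row rules out rounding.** It does not, since 1.696 also rounds up to 1.7.
- **That the SGA N is wrong.** It is not. Liveborn singletons are the planned SGA population.
- **That Fisher's test invalidates the table because it is not the planned analysis.** The footnote names it openly, and Section 7.7.1 does plan a crude relative risk before adjustment. A two-proportion calculation is an ordinary planning approximation and only needs that label for preterm delivery.
- **That stillbirth was overlooked.** Section 7.5 says that power for it is limited and that only high relative risks will be detectable. Any figure would need a rate that the protocol does not give.

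**Conclusion.** The point holds in a narrow form. On Table 4's own inputs, RR 1.4 has about 90% power for preterm delivery and SGA, and the minimum detectable RR at 80% is about 1.34. The stated power is about 10 percentage points too low, or equivalently the stated RR is about 0.06 too high. The direction is conservative and the likely cause is upward rounding.

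For SGA the correction is complete as it stands, because 1,425 is the right population. For preterm delivery, 90% and 1.34 are best-case figures, since 1,425 is an upper bound and the planned model is not a comparison of two proportions. The table does not show that the study is underpowered, and it gives no reason to change the sample size.

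The underived 1,469 is an inconsistency with no practical effect.

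These results rest on the stated 10% and 3% rates, equal groups and an unadjusted two-sided test at 0.05.

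**What to change.** 1. **SGA row:** state RR 1.35 at about 80% power (81.3% exact), or RR 1.4 at about 90%. If RRs are to stay at one decimal, say that they are rounded up and print the power attained.
2. **Preterm row:** make the same correction on an N that reflects the enrollment and vaccination-timing conditions of Section 7.7.1. If that N cannot be projected, state that 1,425 is an upper bound and that the figure is an unadjusted two-proportion approximation to the planned Cox analysis. It would help to add that RR 1.4 retains at least 80% power down to about 1,080 per group on that approximation.
3. **Chorioamnionitis row:** use 1,500, or explain where 1,469 comes from. The detectable RR remains 1.7.
4. Align the sentence that introduces the table, and its title, with the corrected rows.

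The cost is one recalculation and an edit to one table. Study size, conduct and analysis are unchanged.
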